## Title Page

### Study Title

A phase II Randomized Controlled Clinical Trial to assess the effectiveness of Alveolar Recruitment Maneuver (RM) in Improvement of Lung Compliance during Laparoscopic Surgery in Children

### Indication studied

The investigators will test the hypothesis that RM during Abdominal Laparoscopic Surgery in Children aged 1-14 years improves lung compliance and gas exchange. The investigators will apply RM as a Sustained Inflation (at a pressure level of 30 cm H2O for 30 seconds) in pediatric patients under Pressure Controlled Ventilation (PCV) after deflation of pneumoperitoneum.

### Brief description

This will be an Interventional, Prevention, Parallel Assignment, Double-blind (patient, care-giver, outcomes Assessor), Randomized, Safety / Efficacy Study. We will use two parallel groups of children aged 1-14 years who are scheduled for elective Abdominal Laparoscopy

### Trial Site, Patient Enrollment, Start and Completion Date

Trial Site: General Hospital of Thessaloniki "Papageorgiou"

Enrollment: 30 patients

Study Start day: XXXXXXXX

Primary Completion date: XXXXXXXX

Study Completion date: XXXXXXXX

### Protocol Identification

ClinicalTrials.gov Identifier: XXXXXXXX

Study ID Number: XXXXXXXX

### Ethics

The Institutional Review Board will review and approve the study.

This study will be performed in compliance with good clinical practice (GCP): International Conference on Harmonisation of Technical Requirements for Registration of Pharmaceuticals for Human Use - ICH Harmonised Tripartite Guideline - Structure and Content of Clinical Study Reports

### Patient Information and Consent

Written informed consent will be obtained from minors' parents or patients' legally acceptable representatives. Patients will be informed about the trial to the extent compatible with their understanding and, if capable, patients should sign and personally date informed consent form.

### Protocol version

Version: 5.6 (21/9/2017)

## Abbreviations

ASA	American Society of Anesthesiologists Physical Status classification system
BMI	Body Mass Index
CO 2	Carbon dioxide
IAP	Intra-abdominal pressure
IBW	Ideal Body Weight
MinV	Minute Ventilation
MV	Mechanical Ventilation
PACU	Post-Anesthesia Care Unit
PCO 2	Partial Pressure of Carbon Dioxide
PCV	Pressure-controlled Ventilation
PEEP	Positive end-expiratory pressure
P et CO 2	End-tidal carbon dioxide concentration
pH	Power of Hydrogen
PI	Principal investigator
PIP	Peak Inspiratory Pressure
PO 2	Partial Pressure of Oxygen
PO 2 / FiO 2	Arterial Oxygen Partial Pressure to Fraction of Inspired Oxygen
RM	Recruitment Maneuver
RR	Respiratory Rate
SI	Sustained Inflation
SpO 2	Peripheral Oxygen Saturation
Vt	Expiratory Tidal Volume

## Abstract

### Introduction

Pneumoperitoneum and increase in Intra-abdominal Pressure in Children Laparoscopy reduces diaphragmatic excursion and shifts the diaphragm cranially, resulting in the reduction in Lung Compliance and Functional Residual Capacity and Ventilation – Perfusion (V/Q) mismatch leading, finally, to atelectasis, hypoxemia and hypercapnia. In a prospective randomized double-blind clinical trial, the investigators will test the hypothesis that alveolar Recruitment Maneuver (RM) during Laparoscopy in children aged 1-14 years improves Lung Compliance. The primary endpoint of the study will be the improvement in dynamic lung compliance ( $Com_{dyn}$ ) ( $dv/dp$ ) while the improvement in gas exchange (increase in  $PO_2$ ,  $PO_2/FiO_2$ , and decrease in  $PCO_2$ ) will be the secondary endpoint of the study.

### Materials and Methods

Children undergoing Abdominal Laparoscopy will prospectively be assigned to one of two groups. During the operation, patients in both groups, will be ventilated with Pressure-Controlled Ventilation (PCV) with Positive End-Expiratory Pressure (PEEP) 5 cm H2O and titration to achieve Tidal Volume (Vt) 6-7 ml/kg and End-tidal CO2 (EtCO2) 35-40 mmHg. In the RM group, 3 minutes after deflation of pneumoperitoneum, the investigators will apply RM as a Sustained Inflation with CPAP 30 cm H2O for 30 seconds, by setting Manual / Spontaneous Ventilation Mode and the Adjustable Pressure Limitation (APL) Valve to 30 cm H2O. In both groups, lung compliance will be measured (dynamic compliance) as  $dv/dp$  (ml/cm H2O). Measurements (including hemodynamics and blood gas) will be assessed after a stabilization period of Mechanical Ventilation (MV), as baseline before surgical incision, during the pneumoperitoneum, after deflation, after RM and in Post-Anesthesia Care Unit (PACU). A power analysis will be conducted in order to compare Dynamic Lung Compliance ( $dv/dp$ ) between the two study groups. The improvement in Dynamic Compliance will be the Primary Endpoint of the study. Children will be assigned in a 1:1 ratio to one of the two groups using software-generated blocks.

### Results and Discussion

Data will be presented as mean value (+/- SD) and  $p < 0.05$  will be considered significant. The investigators will use Mixed Analysis of Variance to make comparisons between and within groups. At time points before RM is performed, there should be no significant differences in Lung Compliance between the two groups ( $p > 0.05$ ). The investigators will use two-sample t-test as supplementary analysis in order to compare the two groups at each time point, while chi-square test for categorical variables and two-sample t-test for continuous variables for patient and procedural characteristics differences between the two groups will be used. In the RM group, according to similar studies, we expect to detect a significant increase in lung Compliance after RM in comparison to control group where RM will not be applied. In the RM group, the investigators estimate that Dynamic Lung Compliance will be significantly increased compared to baseline compliance too. There should be no significant differences in demographics between the two groups. The investigators expect that there will be no statistical or/and clinical significant differences in patients' hemodynamics and blood gas measurements.

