## Statistical Methods

### Sample size determination

Power Analysis will be conducted for determination of the Sample Size of this study, in order to estimate a Sample Size that is required so that the study would have adequate power to detect clinically meaningful differences between the two groups, especially concerning Lung Compliance (which is the primary outcome of the study).

For this analysis, we used G\*Power Software (version 3.1.9.2), which is freely available at <http://www.gpower.hhu.de/en.html> from the Heinrich-Heine-Universität of Dusseldorf.

Our Power Analysis is based on a published study in literature, from Manner et al. Assuming that Clinically meaningful difference between the two groups is 20% of the mean value and SD of the observed Lung Compliance is 15% of the mean value, therefore Size effect = 0.2 /

0.15 = 1.33, with two-sided testing, with alpha = 0.05 and power = 0.9 (therefore,  $b = 1 - \text{power} = 0.1$ ). Under these assumptions, G\*Power calculated that we will need minimum 13 patients in each group (totally, 26 subjects) for this study to have adequate power.

Assuming a 15% drop-out rate of the initial number of subjects enrolled to this trial, total number of **30** patients will have to be randomized

Alternatively, using the adequate mathematic formula (see Appendix 2) and the results from the Manner et al study, we confirm a minimum Sample Size of 26 patients.

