### Statistical Analysis

[figure not shown]
Investigators will assess data for normality (using Kolmogorov Smirnov and Shapiro Wilks test). Ventilatory and hemodynamic data and intraoperative and postoperative variables (all continuous variables) will be presented as mean values (+/- SD). Data will be compared between and within groups using Mixed Analysis of Variance (Mixed Anova - General Linear Model) if are normally distributed or with Kruskal Wallis test in case that we do not have normally distributed data. Bonferroni correction will be used for multiple comparisons correction. In order to check and supplement our Mixed Analysis of Variance we will also use two-sample t-test to compare the two groups at each time point (for ventilatory and hemodynamic variables). Patient and procedural characteristics will be compared between groups using independent-sample t-test for continuous variables and chi-square test for categorical variables. Two tailed P-values < 0.05 will be considered statistically significant. For data analysis, the investigators will use SPSS statistical software (version 22).

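### With 13 to 15 children per arm, a non-significant haemodynamic test cannot support the expected finding of no haemodynamic difference, and the protocol gives no other criterion for comparing the groups

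*Protocol*

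**What the plan says.** The protocol (Brief description) calls the trial a "Randomized, Safety / Efficacy Study". The abstract's Results and Discussion gives the expected result: "The investigators expect that there will be no statistical or/and clinical significant differences in patients' hemodynamics and blood gas measurements". In the same paragraph, p > 0.05 serves as the mark that the groups have similar compliance before the recruitment maneuver (RM).

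Statistical Analysis makes a mixed ANOVA the main comparison between and within groups, with Kruskal-Wallis for non-normal data. It adds: "we will also use two-sample t-test to compare the two groups at each time point (for ventilatory and hemodynamic variables". The threshold is "Two tailed P-values < 0.05 will be considered statistically significant", and "Bonferroni correction will be used for multiple comparisons correction", with no family defined and no exemption for safety variables. Continuous results are to be shown as mean and SD. No relevant haemodynamic difference, margin or blood-pressure SD is stated.

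The sample size concerns compliance only: "Clinically meaningful difference between the two groups is 20% of the mean value", "SD of the observed Lung Compliance is 15% of the mean value", "with two-sided testing, with alpha = 0.05 and power = 0.9". Limitations of the study says the trial is not powered for pulmonary outcomes such as atelectasis or infection. It does not mention haemodynamics.

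**The concern.** When the hoped-for result is no difference, a difference test rewards imprecision: the fewer the children, the easier it is to obtain p > 0.05. Bonferroni works in the same direction here, because a stricter threshold makes non-significance more likely. The protocol names the expected null, the tests, the threshold and the correction, but not what would count as evidence for that null. A report that follows it could give readers reassurance about haemodynamic effects in children that rests on low power.

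Two other provisions push the same way. The first haemodynamic value after the RM is T5, 3 minutes later (Time points of measurements), so a transient fall during the 30-second maneuver is not in the comparison. Children with severe instability are to be removed from the study (Efficacy and Safety Issues), and a per-protocol analysis applies if most patients complete (Data Presentation Plan). The affected children could therefore drop out of the comparison.

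**Working it through.** **Inputs from the protocol.** Two-sided alpha 0.05; 15 per arm randomised; minimum 13 per arm; compliance effect 0.20/0.15 = 1.33 SD; power 0.90. **Not in the protocol, so assumed:** the true haemodynamic difference (0.3 to 1.33 SD), the Bonferroni family and the within-child correlation r.

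**The plan's own figure.** Two-sample t-test power from the noncentral t, with df = 2n − 2 and noncentrality d√(n/2). At d = 1.33, n = 12 gives 87.6% and n = 13 gives 90.2%. The stated 13 per arm reproduces.

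**Precision, which needs no assumed effect.** Half-width of the 95% interval in SD units = t(0.975, 2n − 2) × √(2/n).

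- n = 15: 2.048 × 0.3651 = 0.75 SD
- n = 13: 2.064 × 0.3922 = 0.81 SD

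With 15 per arm, an observed difference of zero is thus compatible with a true fall of up to 0.75 SD. If the SD of systolic pressure is assumed to be 10 to 20 mmHg, that is 7.5 to 15 mmHg.

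**Probability that the t-test at one time point is non-significant.** Example: n = 15, d = 0.5 gives noncentrality 0.5 × √7.5 = 1.369 against a critical value of 2.048. Power is 26%, so 74% are missed.

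| True difference (assumed) | 15 per arm | 13 per arm |
|---|---|---|
| 0.3 SD | 87.5% | 89% |
| 0.5 SD | 74% | 77% |
| 0.8 SD | 44% | 50% |
| 1.0 SD | 25% | 31% |
| 1.33 SD | 6% | 10% |

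**With Bonferroni (15 per arm, 0.5 SD).** If the family is T5 and T6, alpha = 0.025 and the miss rate is 82%. If it is all nine haemodynamic time points, alpha = 0.05/9 = 0.0056 and the miss rate is 93%.

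**Using the earlier value.** With r = 0.7 assumed and T4c as covariate (27 df), the half-width falls to 2.052 × 0.3651 × √(1 − 0.49) = 0.54 SD. A change-score contrast has effect 0.5/√(2 × 0.3) = 0.645 and misses a 0.5-SD difference 60% of the time. At r = 0.5 the change score gains nothing, because √(2 × 0.5) = 1.

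**Events.** With 0 events in 15 children, the exact one-sided 95% upper bound is 1 − 0.05^(1/15) = 18%.

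**The case against.** A reader might infer that the protocol makes p > 0.05 its safety decision rule. It does not. The sentence in the abstract is an expectation, it refers to clinical as well as statistical significance, and no passage says that safety will be concluded from non-significance. Safety is also handled elsewhere: age-specific individual limits (Removal of Patients from Therapy), beat-to-beat arterial monitoring (Efficacy and Safety Issues), recording of hypotension, bradycardia and desaturation (Adverse Events), and an independent data monitoring committee. These safeguards stand. They govern conduct, however, and none says how the between-group result is to be interpreted.

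A reader might also take from the 0.5-SD row that a relevant fall would be missed about three times in four. That needs a relevant fall of about 0.5 SD, which the documents do not state; at 1.0 SD the difference is detected three times in four. The figures are also for the supplementary t-test. The main mixed ANOVA uses repeated values within a child and may do better if the correlation is high. The 93% figure depends on an assumed family of nine time points, seven of which precede the RM.

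Haemodynamics are secondary measurements, and a trial of 30 need not be powered for each of them. That is fair, and no larger sample is asked for. Finally, confidence intervals and covariates are often left to a statistical analysis plan, so their absence alone would be no finding. What remains is what this protocol does fix: an expected null, a difference test and an unrestricted Bonferroni correction, which together cannot support that null.

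**Conclusion.** The point holds in limited form. Non-significance with 13 to 15 children per arm cannot support the haemodynamic result that the abstract expects, and the protocol supplies no other criterion for the group comparison. The firmest measure is the interval half-width of 0.75 to 0.81 SD, which assumes only an unadjusted two-sample comparison. The miss rates, 87.5% to 6% over 0.3 to 1.33 SD with 15 per arm, depend on an effect size that the documents leave open. They fall if r is high and the earlier value is used, and rise under Bonferroni. The documents do not show that safety will be declared from p > 0.05, nor do they support any single miss rate for a relevant fall.

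**What to change.** In Statistical Analysis, add wording to this effect:

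*For SBP, MAP and HR at T5 and T6, the RM-minus-control difference, adjusted for the T4c value, is reported with an unadjusted 95% confidence interval. Bonferroni correction is not applied to safety comparisons. A p-value above 0.05 is not read as absence of an effect. Hypotension, bradycardia and desaturation are reported per arm, counting all randomised children including those removed for instability, with exact 95% upper bounds.*

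Reword the haemodynamic part of the abstract's sentence to match. In Limitations of the study, add haemodynamic safety to what the trial is not powered to show, and state that T5 does not capture a transient fall during the maneuver. A prespecified margin is optional and for the clinical investigators to set.

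Before T4c is used as covariate, confirm that it precedes the RM: the time-point table places it before, while Blinding Procedure places T4 after the RM. The two must be reconciled.

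The cost is wording only. The haemodynamic values are already recorded in Appendix 5 and the events under Adverse Events, so no extra patients or procedures are needed. The downside is a less favourable haemodynamic safety statement, which will probably be inconclusive. The gap during the maneuver itself is disclosed but not closed.

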## Introduction

### Recruitment Maneuver – Definition

Alveolar recruitment maneuver (RM) is a technique using sustained airway pressure increase aiming at recruiting collapse alveoli, increasing lung area available for gas exchange and consequently improving arterial oxygenation.

### General Anesthesia, Atelectasis and Recruitment Maneuver

Mechanical ventilation (MV), during General Anesthesia (GA), should not be considered as a simple and neutral intervention, without potential serious consequences in patient's homeostasis. In fact, Positive Pressure MV is increasingly recognized as a potentially harmful intervention that can cause lung damage (Ventilator-Induced Lung Injury – VILI) and respiratory muscle injury (Ventilator-Induced Diaphragm Dysfunction - VIDD).

Between the several mechanisms that have been postulated to describe the development of VILI, Atelectasis plays an important role, as in the presence of atelectasis, MV may harm the alveolar units by repetitive collapse and reopening, a condition that is called atelectrauma.

Atelectasis develops in as much as 90% of patients undergoing general anesthesia and can be present to different degrees after surgery, maybe for days. It occurs in the dependent parts of the lungs and the development of atelectasis is associated with several pathophysiologic effects, including decreased lung compliance, impairment of oxygenation and increased pulmonary vascular resistance. Atelectasis is a major cause of intra- and post- operative hypoxemia while it also predisposes to postoperative lung infections.

The consequences of atelectasis persist into the postoperative period and can influence patient recovery; over the last years there is growing evidence that an intraoperative lung-protective mechanical ventilation strategy, using low Tidal Volumes (Vts), with or without high levels of Positive End-Expiratory Pressure (PEEP) and Recruitment Maneuvers (RMs), prevents Post-operative Pulmonary Complications (PPCs).

### Laparoscopic Surgery in Adults and Children

In the recent years, advances in laparoscopic technique and refinement in the equipment have led to a significant increase in the use of Laparoscopy in Children, offering its benefits to young patients. In comparison to conventional open technique, Laparoscopy is related with reduced surgical trauma, less postoperative pain, reduced perioperative morbidity, earlier postoperative mobilization, shorter hospital stays and better cosmetic results.

Nevertheless, from the anesthetic point of view, Laparoscopic Surgery exposes the patient to additional physiological modifications and thus potential risks. Laparoscopic Surgery involves the intraperitoneal insufflation of carbon dioxide (CO2) to permit adequate visualization and manipulation of the abdominal viscera. The pneumoperitoneum, except the CO2 absorption, involves an increase in the Intraabdominal Pressure (IAP), which, among other, can have significant cardiovascular, respiratory and neurological effects. A thorough understanding of the pathophysiological changes mentioned above is crucial for optimal anesthetic care.

### CO2 Absorption effects

During intraperitoneal insufflation, CO2 diffuses to the body and its diffusion leads to increased PaCO2 (tension of carbon dioxide in arterial blood) values in the intra- and post-operative period. Hypercapnia constitutes a strong stimulus for Minute Ventilation (MinV) to increase, by as much as 60%, to normalize the End-tidal CO2 (EtCO2) while it activates the sympathetic nervous system leading to an increase in blood pressure, heart rate, myocardial contractility, and arrhythmias. It also sensitizes the myocardium to catecholamines, particularly when volatile anesthetic agents are used.

### Hemodynamics during Laparoscopy

Main hemodynamic changes include alterations in arterial blood pressure (i.e., hypotension and hypertension) and arrhythmias. The extent of the cardiovascular changes associated with creation of pneumoperitoneum depends on the level of IAP, volume of CO2 absorbed, patient's intravascular volume, ventilatory technique, surgical conditions and anesthetic agents used. However, the most important determinants of cardiovascular function during laparoscopy are the IAP and patient position.

### Pulmonary Function during Laparoscopy

Changes in pulmonary function during laparoscopy include reduction in lung volumes, increase in peak airway pressures, and decrease in pulmonary compliance, secondary to increased IAP and patient positioning.

Creation of pneumoperitoneum at an IAP of 15 mm Hg reduces respiratory system compliance and increases peak inspiratory and mean airway pressures. Elevated IAP reduces diaphragmatic excursion and shifts the diaphragm cranially, resulting in early closure of smaller airways leading to intraoperative atelectasis with a decrease in functional residual capacity. On one hand, upward displacement of the diaphragm leads to preferential ventilation of nondependent parts of the lung, which results in ventilation-perfusion (V/Q) mismatch with a higher degree of intrapulmonary shunting, whereas on the other, it leads to endobronchial intubation. These pulmonary pathophysiological changes lead to hypercapnia and hypoxemia, in case of non-effective ventilation, and to pulmonary vasoconstriction

Blood gas changes and respiratory mechanics are affected by the duration of pneumoperitoneum and patient positioning. The deterioration in respiratory function is reduced when the patient is in the reverse Trendelenburg position and worse when the patient is in the Trendelenburg position.

### Ventilation strategy during Laparoscopy

The above physiological modifications during Laparoscopy, have been already extensively studied both for adults and for children.

Regarding adult patients, the reasonable idea of using during Laparoscopy a Ventilatory Strategy closer to Protective Ventilation Strategies (with low Vt, PEEP and RM) has been already studied with positive results.

On the contrary, while RM has been extensively studied in the context of Pediatric Intensive Care Units (PICUs) with positive results as well, there is a paucity in literature about performing RM during Laparoscopic Surgery in Children.

## Study Objectives

In this study, overall, we will test the hypothesis that the application of RM after deflation of pneumoperitoneum during Abdominal Laparoscopy in Children improves Lung Dynamic Compliance ( $Com_{dyn}$ ) and Perioperative Oxygenation. In this study, we aim to suggest that the Recruitment Maneuver could reverse Lung Atelectasis which is a major cause for respiratory complications intra- and post-operatively.

## Investigational Plan

### Study population and Control Group

This will be a Prospective, Randomized, Double-blind, Controlled Clinical Trial. After approval of the Institutional Ethics Committee (Papageorgiou General Hospital of Thessaloniki, Scientific and Ethic Committee), this trial will be conducted at Papageorgiou General Hospital, starting from XXXX XXXX. After having obtained written informed consent for the participation in the study (see below: Ethics), 30 children (the number originates from the power analysis – see below) with American Society of Anesthesiology Classification scores (ASA) 1 – 2 will be scheduled for Abdominal Laparoscopic Surgery. The Control Group will be managed with a more conventional anesthetic practice (no recruitment, moderate levels of PEEP). This will be a non-treatment concurrent control trial.

